### 7.1.3.5 PROMIS(®) Fatigue Short Form

The PROMIS Fatigue Short Form measure is an 8-item self-administered questionnaire assessing the extent of fatigue and its impact on work and functioning in the last 7 days. Each question is scored between 1 and 5 (See Appendix C - **PROMIS(®) Fatigue Short Form** for scoring conversion) and a total raw score will be calculated by summing the values of the response to each question. A standardised T-Score will then be calculated by standardizing the raw total score to a scale with mean 50 and SD 10 (See Appendix C - **PROMIS(®) Fatigue Short Form** for conversion tables).

If between 1 and 4 items (inclusive) have a missing response then the raw total score will be estimated from the non-missing responses using the below formula:

$$\text{Total Raw Score} = \frac{\text{Sum of scores of items answered} \times 8}{\text{Number of items answered}}$$

If the result is a fraction, round up to the nearest whole number. If greater than 4 items have a

---

missing response then the total raw score will not be calculated

### **7.1.3.6 Brief Fatigue Inventory (BFI)**

The BFI is an 9-item self-administered questionnaire, providing an assessment of the severity of fatigue and its impact on the subject's ability to function at present and in the previous 24 hours. A global fatigue score is calculated by deriving the mean score of each of the non-missing questions.

If more than 4 questions have a missing response, then the global fatigue score will not be calculated

### **7.1.3.7 36-Item Short Form Health Survey (SF-36)**

The SF-36 questionnaire is a multidimensional instrument that evaluates quality of life. It measures 8 general health concepts or domains: Vitality, Physical Functioning, Bodily Pain, General Health Perceptions, Physical Role Functioning, Emotional Role Functioning, Social Role Functioning and Mental Health. These domains will also be summarised as physical and mental component scores. Please see

Appendix D - **36-Item Short Form Health Survey (SF-36)** for detailed scoring of each domain and component scores.

### 7.1.3.8 Patient Global Impression of Status items (PGI-S)

Three patient global impression items will be included to assess the patients' overall impression of their current health status and thus to evaluate the performance of the other PROs in this patient population. Each response will be converted to a numeric score for summarising using the below conversions:

Response	Score
Not at all	1
A little bit	2
Somewhat	3
Quite a bit	4
Very much	5

### 7.1.3.9 Actigraphy Derived Activity and Sleep Parameters

The Autograph Link is a portable device that measures gross motor movements featuring a validated 3-axis accelerometer and data filtering technology that captures and records continuous, high resolution physical activity and sleep/wake information.

Subjects are instructed to wear the monitor for 7 days consecutively starting with the day of the scheduled Visit 1 (if not collected as part of the EOT assessment for MBGS205), and Visit 7 (EOT). Only data collected during the specified visit windows (See Appendix E – Actigraphy Visit Windows) on days where the device had been worn for  $\geq 1152$  minutes (i.e 80% daily compliance) and deemed (either algorithmically or hardware detected by the device) to have been collected while the device was being worn will be used. All evaluable data within the specified visit window will be used to derive each parameter at each visit. However if there are less than 3 evaluable days' worth of data collected within the window the parameter will be set to missing.

#### Activity Parameters

The average number of minutes spent per day within each activity category below will be calculated for each visit:

- Sedentary
- Light

- Lifestyle
- Moderate
- Vigorous
- Very Vigorous
- MVPA (Moderate to Very Vigorous Physical Activity)

In addition the average daily total number of steps and total activity counts (across all 3 axis) will be calculated as well as the maximum daily total activity count across each visit.

### Sleep Parameters

The average length of awakenings (minutes), number of awakenings, number of minutes asleep (minutes), number of minutes awake (minutes) and proportion of time spent asleep during the sleep period will be calculated per day for each scheduled visit. Sleep periods starting before 5am will be assigned to the previous day.

#### **7.1.3.10 Grip Strength**

Grip strength assessment using a hand held dynamometer will be used as a surrogate measure of muscle strength. During this assessment, the subject will squeeze the device three times with each hand. An average (mean) of three measurements for each hand will be calculated at each visit.

#### **7.1.3.11 Metabolic syndrome (APP III) Definition**

A subject will be deemed as meeting the definition of metabolic syndrome if they meet 3 out of 5 the below criteria at the same visit:

- Waist Circumference >102cm (>40inches)
- Triglycerides > 150mg/dl (>1.69 mmol/L)
- HDL Cholesterol <40mg/dl (<1.036 mmol/L)
- Blood pressure >130mmHg (systolic) or >85mmHg (diastolic)
- Glucose >110 mg/dl (>6.11 mmol/L)

### **7.1.4 Definitions relative to safety parameters**

#### **7.1.4.1 Adverse Event (AE)**

##### Treatment Emergent Adverse Event (TEAE)

A Treatment Emergent AE (TEAE) is defined as an AE occurring or worsening on or after the first dose of active study medication (from either MBGS205 or MBGS206).

TEAEs will also be split between AEs that start during the subject's active treatment period (for subjects randomised to active in MBGS205 this includes AE's starting in study MBGS205) and those that start on or after the first day of the MBGS206 follow-up period. A further category of TEAEs that started in MBGS206 but prior to the MBGS206 follow up period will also be utilised for summary tables (TEAEs started in MBGS205 would be excluded from this category).

### Duration of AEs

The duration of an AE will be calculated as the resolution date minus the start date plus 1.

#### **7.1.4.2 Treatment Compliance**

##### Duration of Exposure

The duration of Exposure to active study medication over both MBGS205 and MBGS206 (number of days) will be defined as:

[figure not shown]
(date of last dose of active study medication – date of first dose of active study medication) + 1

The duration of Exposure to MBGS206 study medication (number of days) will be defined as:

[figure not shown]
(date of last dose of MBGS206 study medication – date of first dose of MBGS206 study medication) + 1

##### Treatment Compliance

Overall (MBGS205 and MBGS206) active treatment compliance will be defined as:

MBGS206 treatment compliance will be defined as:

#### **7.1.4.3 Prior, Concomitant and Follow-up Medications/Procedures**

Medications and Procedures will be assigned as being prior to active study medication, concomitant with active study treatment or taken during the follow-up phase based on the start and stop dates of the medication and dosing dates.

If the medication/procedure stop date is before the date of the first active study medication (for subjects randomised to Placebo in MBGS205, this includes medication/procedures starting in study MBGS205), the medication/procedure will be assigned as being prior to active study medication. Otherwise, the medication/procedure will be assigned as being concomitant with active study treatment (for subjects randomised to active in MBGS205, this includes medications/procedures starting in study MBGS205) unless the start date of the medication/procedure is after the MBGS206 end of treatment date, when it will then be classified as occurring in the follow-up

phase.

In addition medications will be flagged as being concomitant during the MBGS206 treatment period (i.e medication started on or after the first dose of MBGS206 study medication but before the follow up period or was ongoing at MBGS206 baseline).

#### 7.1.4.4 Osteopenia and Osteoporosis

DXA Scans assessments for each region (Spine and Hip) will be assigned into the below severity categories:

- Normal: (T score >-1.0 )
- Osteopenia: (T Score between -1.0 and -2.5)
- Osteoporosis: (T score < -2.5 or Z-Score (under 50 years) <-2.0)

#### 7.1.4.5 Potential Hy's Law Criteria

Subjects will be deemed as meeting potential Hy's law Criteria if their ALT or AST > 3x ULN and bilirubin > 2 x ULN at the same visit.

#### 7.1.4.6 Estimate Glomerular Filtration Rate (eGFR)

A derived calculation of eGFR will be calculated using the 4 variable Modification of Diet in Renal Disease (MDRD) equation (Lavey 1999 and 2000):

$$\text{eGFR (mL/min/1.73m}^2\text{)} = 175 (\text{Serum Creatinine in } \mu\text{mol/l} \times 0.011312)^{-1.154} \times (\text{age})^{-0.203} \times (0.742 \text{ if female}) \times (1.212 \text{ if African/American Black})$$

This derivation will be used as a supportive analysis to the eGFR as derived by the lab.

## 7.2 Handling of missing data and outliers

### 7.2.1 Missing data analysis methods

Unless specified, data in summary tables will be presented using Observed Case (OC) data and therefore no missing data will be imputed.

For specified endpoints a last observation carried forward (LOCF) imputation will be utilised. In this approach subjects with a missing observed value at a visit will be imputed with the last non-missing, post-baseline value.

For each continuous exploratory endpoint, the change from Baseline will be assessed with a mixed model repeated measure (MMRM) analysis.

For data listings, unless specified, all data will be presented as they have been recorded (e.g. missing and partial dates will not be replaced).

---

### 7.2.2 Handling of missing or incomplete data

#### 7.2.2.1 Partial dates of first HH diagnosis

In order to calculate the HH disease duration (i.e. time since first HH diagnosis), the following rules will be applied for partial dates for first diagnosis of HH:

- if the day of the month is missing it is imputed to be the 15th
- if both the day and month are missing, they are imputed to be June 30th
- missing years will be left as missing.

The above will be flagged and described as a footnote in the appropriate listings.

#### 7.2.2.2 Missing items within Questionnaire data

The method of handling missing data for each questionnaire will be based upon the author's recommendation. Details can be found in Section 7.1.3.

#### 7.2.2.3 Missing or incomplete concomitant medication dates

Should the start date for a medication/procedure be missing or incomplete to the extent that it could be before or after the time of start of MBGS206 study medication, then it will be assumed that the medication/procedure began after the start of MBGS206 study medication (i.e. reported as concomitant medication/procedure). Similarly, if it is not clear whether the medication/procedure start date was on or before, or after the Visit 7 date, then it will be assumed the medication/procedure began on or before the Visit 7 date (i.e. reported as a concomitant medication/procedure) (worst case approach).

#### 7.2.2.4 Definition of treatment-emergent AEs and handling of missing or incomplete dates

In the event of an incomplete onset date, the event will be considered to be treatment-emergent unless the partial onset date information or complete or partial end date confirms onset or end prior to the first dose of active study medication date.

## 8 STATISTICAL METHODS

### 8.1 General statistical conventions

All statistical procedures will be completed using SAS version 9.4 or higher.

#### 8.1.1 Populations for analysis

Demographic and baseline characteristics will be summarised by Safety, Completers and ITT populations, unless otherwise stated.

Analyses of the primary endpoint and secondary safety BMD endpoints will be performed on ITT and completer population. Analysis of all other safety endpoints will use the safety population.

The secondary efficacy endpoints and exploratory endpoints will be analysed using the ITT population.

The safety and tolerability variables will be analysed using the Safety population.

PK data will be analysed using the PK population.

#### 8.1.2 Treatment groups

Statistics will be displayed for the following treatment regimens in the below order:

- BGS649 [REDACTED]
- BGS649 [REDACTED]
- BGS649 [REDACTED]
- Active Total (Includes all continuous active groups where applicable)
- Placebo -> BGS649 [REDACTED]
- Placebo -> BGS649 [REDACTED]
- Placebo -> BGS649 [REDACTED]
- Plabebo-> Active Total (Includes all Placebo-> Active Groups where applicable)
- Overall Total (Includes all groups where applicable)

#### 8.1.3 Descriptive statistics

Continuous variables will be summarised using descriptive statistics including number of non-missing observations (n), arithmetic mean (Mean), median (Median), standard deviation (SD), minimum value (Min) , maximum value (Max) and number of missing observations (if any). One additional decimal point for mean and median and 2 additional decimal points for SD will be used.

For categorical variables, summaries will include the number of non-missing observations (n) or the number of patients in the population (N) as applicable, the counts of subjects and percentages. Percentages will be rounded to one decimal place. The number of missing values will be presented as a separate category with no percentage, but only if any missing value is recorded in the data for that summary.

Summary statistics will only be presented at each visit for which the parameter is scheduled to be

collected.

### 8.1.4 Statistical significance

Unless otherwise stated, all statistical testing will be two-sided and conducted at the significance (alpha) level of 0.05. Two-sided 95% confidence intervals (CIs) will be provided when relevant. Treatment regimens will be assessed by pairwise comparisons, and no adjustment for multiplicity will be made.

### 8.1.5 Definition of Baseline

For summary purposes, the baseline value is defined as the last non-missing value collected on or before the first active study treatment administration (from either Study MBGS205 or MBGS206). Therefore subjects randomised to active treatment in Study MBGS205, baseline will be the last value prior to first dose of study medication in Study MBGS205. For subjects randomised to placebo in Study MBGS205, baseline will be the last value prior to first dose of study medication in Study MBGS206 (expected to be from the MBGS206 baseline visit)..

Change from Baseline is defined as (value at assessment date – baseline value).

For DXA parameters, assessments at MBGS205 baseline can be taken up to 8 days after the Baseline Visit. As such baseline will be defined as the last non-missing value collected up to 8 days post the date of first dose of study medication for subjects randomised to active treatment in Study MBGS205).

For selected renal parameters change from MBGS205 Screening and Baseline will be calculated. Change from Screening will be defined as (value at assessment date – screening value), where the screening value is defined as the last non-missing value collected at a Screening Visit (Day -28 to Day -1).

### 8.1.6 Data re-allocation

The following general rules to handle repeated assessments will be considered:

- 12-lead ECG:
  - in case of multiple measurements associated to the same timepoint (e.g. triplicate ECGs), the average value will be considered for all post baseline HR, RR interval, PR interval, QRS duration, QT interval, QTcB interval and QTcF interval.

### 8.1.7 Data listings

All relevant subject data collected during the MBGS206 study, including those derived will be presented in individual subject data listings. Selected data from study MBGS205 will also be presented to aid in interpretation (e.g MBGS205 baseline) All listings will be sorted by treatment regimen, investigational site, subject number, date/time and visit. The subject's age will be stated on each listing. Unless otherwise stated, data listings will be based on all subjects randomised.

Unscheduled visit results will be included in date/time chronological order within subject listings, but will not be tabulated.

---

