4. Total testosterone \geq 1500 ng/dL (52 nmol/L) at any 2 consecutive scheduled visits during and in between the both studies MBGS205 and MBGS206. This would also include situation when first testosterone value that meets this threshold of \geq 1500 ng/dL

[52 nmol/L] was measured during MBGS205 and consecutive testosterone during Study MBGS206.

5. Liver laboratory values of:

- ALT or AST > 5 times the ULN

If the increase in ALT or AST is associated with normal bilirubin and ALP, the medical evaluation of withdrawing a subject can be made on a repeat AST/ALT test taken within 48 hours. (Repeated parameters should include: ALT, AST, alkaline phosphatase and total bilirubin). The subject should interrupt study drug until the repeat liver enzymes are available. If repeat liver parameters are all within the normal range, dosing may be continued. If not normalised the subject should be permanently discontinued.

or

- ALT or AST > 3 times the ULN and bilirubin total > 2 times ULN or International Normalised Ratio (INR) > 1.5 or the appearance of worsening fatigue, nausea, vomiting, right upper quadrant pain/tenderness, fever, rash, or eosinophilia
- A hepatic event leading to subject discontinuation should be followed up until event resolution, or becomes not clinically significant

6. Any of the following laboratory abnormalities:

- Renal function values that require discontinuation:
 - Discontinue investigational treatment for a subject if individual serum creatinine increases $\geq 50\%$ compared to Baseline (and is considered clinically significant), or in the event of treatment emergent proteinuria (albumin: creatinine ratio > 300 mg/g or > 30 mg/mmol; protein: creatinine ratio ≥ 500 mg/g or > 50 mg/mmol) (Creatinine can be repeated once within 7 days of initial alert. Study drug administration should be suspended during this time and resumed only if repeat creatinine is back to pre-alert level)
 - A renal event leading to subject discontinuation should be followed up until event resolution (serum creatinine within 10% of Baseline, protein-creatinine ratio within 50% of Baseline), stabilises or becomes not clinically significant, or is assessed as being chronic

7. Subject missed 4 or more consecutive study drug dosing

8. Development of prostate cancer or PSA increase more than 1.4 ng/mL above Baseline level in study MBGS205. It is recommended that in these cases subjects undergo urologic consultation

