AE=adverse event; AESI=adverse event of special interest; BFI=Brief Fatigue Inventory; BMI=body mass index; CTx1=C-terminal telopeptide; D=day; DEXA=dual energy X-ray absorptiometry; DBP=diastolic blood pressure; ECG=electrocardiogram; eGFR=estimated glomerular filtration rate; EOT=End of Treatment; FSH=follicle stimulating hormone; FU=Follow-Up; HbA1c=glycosylated haemoglobin; HDL=high density lipoprotein; HOMA-IR=homeostatic assessment of insulin resistance; hs-CRP=high sensitivity C-reactive protein; IIEF=International Index of Erectile Function; LDL=low density lipoprotein; LH=luteinising hormone; P1NP=procollagen type 1 N-propeptide; PGI-S=Patient Global Impression of Status; PK=pharmacokinetics; PRO=patient reported outcome; PROMIS=Patient-Reported Outcomes Measurement Information System; PSA=prostate-specific antigen; QoL=quality of life; RBC=red blood cell; SAE=serious adverse event; SBP=systolic blood pressure; SexFS= Sexual Function and Satisfaction; SF-36=36-item Short Form Health Survey; SHBG=sex hormone binding globulin; W=Week; WBC=white blood cell.

- 1 Baseline assessment will be performed on a same day as the EOT visit of Study MBGS205. As applicable, EOT assessments of Study MBGS205 will be used for Baseline assessments of Study MBGS206 and do not need to be repeated. The results of liver enzymes, PSA, haematocrit, and ECG assessments performed at the Baseline visit will not be available for eligibility assessment, therefore results of these parameters from last valid visit of Study MBGS205 will be used. This includes any of these parameters from last scheduled or unscheduled visit measure but no longer than 1 month before Baseline visit/EOT of MBGS205 .
- 2 Only subjects receiving placebo in Study MBGS205 to be randomised. Subjects already on active in Study MBGS205 will maintain their treatment allocation
- 3 All blood samples are to be collected after 8 hours fasting, after ECG and vital sign measurements have been performed
- 4 A microscopic examination including RBC and WBC or urinary protein will be performed only when dipstick evaluation is positive for WBC and/or blood or protein
- 5 Bone turnover markers include CTx1, osteocalcin, bone alkaline phosphatase, and P1NP
- 6 Has to be collected before 11 am. If the sample was inadvertently taken after this time, a retest is allowed after a discussion with the Medical Monitor.

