### 4.2 Secondary Endpoints

#### 4.2.1 Secondary Safety Endpoints

1. In subjects that were randomized to active treatment in Study MBGS205 by dose group:
  - o Percentage change in hip (total and femoral neck) bone mineral density measured by DEXA (g/cm^2) from Baseline in Study MBGS205 to Week 48 in Study MBGS206
  - o Percentage change in bone turnover markers (C-terminal telopeptide [CTx1], osteocalcin, bone alkaline phosphatase, and procollagen type 1 N-propeptide [P1NP]) from Baseline in Study MBGS205 to Week 48 in Study MBGS206
  - o Proportion of subjects with T-scores  $\leq$  -2.5 at Week 48
  - o Percentage change in bone density and bone biomarkers adjusted for vitamin D deficiency from Baseline in Study MBGS205 to Week 48 in Study MBGS206
  - o Change of oestradiol (absolute and percentage) from Baseline in Study MBGS205 to Week 48
  - o Proportion of subjects that overshoot testosterone (total testosterone above 1000 ng/dl [35 nmol/L], from first dose of study drug in Study MBGS205 until study completion)
  - o Change in PSA from Baseline in Study MBGS205 to Week 48 in Study MBGS206
  - o Change in haematocrit from Baseline in Study MBGS205 to Week 48 in Study MBGS206
  - o Change in blood pressure (systolic and diastolic) Baseline in Study MBGS205 to Week 48 in Study MBGS206
  - o Treatment emerged AE, SAE, and AESI (from first dose of study drug in Study MBGS205 until study completion)
  - o Relationship between change in bone mineral density from Baseline in Study MBGS205 to Week 48 in Study MBGS206 and absolute levels of oestradiol and total testosterone at Week 48 in MBGS206

2. In subjects that were randomized to placebo in Study MBGS205 by dose group:
  - o Percentage change in lumbar bone mineral density measured by DEXA (g/cm^2) from Baseline in Study MBGS206 to Week 48
  - o Percentage change in hip (total and femoral neck) bone mineral density measured by DEXA (g/cm^2) from Baseline in Study MBGS206 to Week 48
  - o Percentage change in bone turnover markers (CTx1, osteocalcin, bone alkaline phosphatase, and P1NP) from Baseline in Study MBGS206 to Week 48
  - o Change of oestradiol (absolute and percentage) from Baseline in Study MBGS206 to Week 48
  - o Proportion of subjects with T-scores  $\leq -2.5$  at Week 48 of Study MBGS206

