### 8.6.3.4 Proportion of subjects that Overshoot Testosterone

The number and proportion of subjects that overshoot testosterone (total testosterone above 1000 ng/dL [35 nmol/L]) at each visit and at least once during the study will be summarised similar to that of Testosterone normalisation.

In addition the number and proportion of subjects whose maximum testosterone value falls into each of the below categories will be presented by visit and overall during the study:

- >1000 - <=1500ng/dl
- >1500 – <1800 ng/dL
- =>1800 - <= 2500 ng/dL
- >2500 ng/dL

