### **8.7.5.2 Liver Function**

The number and proportion of subjects with laboratory values for liver function and enzymes of clinical concern as follows will be presented descriptively by treatment regimen:

Parameter	Level for clinical concern
ALT	> 1.5 times the upper limit of the normal range (ULN) > 2xULN > 3xULN > 5xULN > 10xULN
AST	> 1.5xULN > 2xULN > 3xULN > 5xULN > 10xULN
Bilirubin Total	> 2xULN > 3xULN
ALT/AST and Bilirubin Total	ALT/AST > 3xULN and Bilirubin Total > 2xULN (assessments to occur at the same visit)

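### SAP 8.1.7 keeps unscheduled results out of tables without exception, so the liver-threshold and potential Hy's-law counts can miss events first seen at the protocol's own liver repeat

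*SAP*

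**What the plan says.** SAP 8.1.7 (Data listings) gives the rule: "Unscheduled visit results will be included in date/time chronological order within subject listings, but will not be tabulated". SAP 8.1.3 points the same way: "Summary statistics will only be presented at each visit for which the parameter is scheduled to be" collected.

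Three parts of the SAP define counts over a subject's whole follow-up, and none of them mentions unscheduled results:

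- **Liver (8.7.5.2).** "The number and proportion of subjects with laboratory values for liver function and enzymes of clinical concern as follows will be presented descriptively", for each arm. The levels run from 1.5x to 10xULN for ALT and AST, and 2x and 3xULN for total bilirubin, plus the combined ALT/AST and bilirubin criterion.
- **Potential Hy's law (7.1.4.5).** ALT or AST above 3xULN and bilirubin above 2xULN, both at one visit.
- **Testosterone overshoot (8.6.3.4).** Overshoot "at each visit and at least once during the study will be summarised similar to that of Testosterone normalisation", and the number of subjects whose "maximum testosterone value falls into each of the below categories will be presented by visit and overall during the study". For subjects on active drug in the parent study, SAP 4.2.1 sets the period of this endpoint: "from first dose of study drug in Study MBGS205 until study completion".

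The protocol itself creates tests off the schedule. Under the ALT/AST above 5xULN criterion in Protocol 9.3.4, when bilirubin and alkaline phosphatase are normal, "the medical evaluation of withdrawing a subject can be made on a repeat AST/ALT test taken within 48 hours". The repeat panel includes total bilirubin. For testosterone, which must be drawn before 11 am, the footnote to SAP Table 1 says: "If the sample was inadvertently taken after this time, a retest is allowed after a discussion with the Medical Monitor". The only repeat-assessment rule in SAP 8.1.6 is for ECGs.

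**The concern.** Leaving unscheduled values out of by-visit means is sound practice, because those values come from subjects selected for being abnormal. Applied to a count of subjects who ever reach a threshold, the same rule works against its purpose. Such a count should find the worst value seen, and the off-schedule tests are taken in the subjects most likely to have it.

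At stake is the liver summary of a six-month safety extension with about 30 continuing subjects per dose, where one case changes how an arm reads. A smaller issue is that the normalisation analysis could rest on a testosterone sample drawn at the wrong time, because nothing says which value is used when a retest exists.

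**Working it through.** The plan gives no figure to reproduce here. The check sets the rules side by side and then illustrates the size.

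**1. Direction.** Let S be a subject's scheduled results and U the unscheduled ones. Then max(S) ≤ max(S and U together), and any threshold crossed in S is also crossed in the combined set. Leaving out U can therefore only lower, or leave unchanged, the number of subjects at or above a given threshold.

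**2. The liver pathway.**

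- Routine chemistry is scheduled at Weeks 28, 32, 36, 40, 44, 48 and 60, so a repeat within 48 hours is normally off schedule.
- The repeat is offered when ALT or AST exceeds 5xULN and bilirubin and alkaline phosphatase are normal.
- At the triggering visit, then, ALT/AST above 3xULN is met, but bilirubin is normal and so not above 2xULN. The combined criterion fails there by construction.
- The repeat measures ALT, AST and bilirubin together. It is the first test on this pathway at which the combined criterion, or a bilirubin-only level, could be met.
- If the triggering ALT or AST lies between 5x and 10xULN, a first value above 10xULN can likewise appear at the repeat.
- SAP 8.1.7 lists that repeat but does not tabulate it.

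| Count in SAP 8.7.5.2 | Triggering scheduled visit | May first be met at the repeat |
|---|---|---|
| ALT/AST >1.5x, >2x, >3x, >5x | already counted for the enzyme that triggered | no |
| ALT/AST >10x | only if the trigger is already that high | yes |
| Bilirubin >2x, >3x | not possible | yes |
| ALT/AST >3x with bilirubin >2x | not possible | yes |

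**3. Testosterone counts.** The endpoint covers first dose to study completion, while 8.1.3 and 8.1.7 confine its at-least-once and overall-maximum counts to scheduled results. The protocol has no repeat test for a high value: Protocol 9.3.4 uses two consecutive scheduled visits. The late-sample retest is therefore the only off-schedule route the protocol provides.

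**4. Size, as an illustration.** Protocol 13.1 and SAP 3.1 plan 30 subjects per continuing active arm, so 3 x 30 = 90 in all. Intervals are exact 95%.

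| Group | None counted | One added |
|---|---|---|
| Arm of 30 | 0/30 = 0% (0 to 11.6%) | 1/30 = 3.3% (0.1 to 17.2%) |
| 90 continuing subjects | 0/90 = 0% (0 to 4.0%) | 1/90 = 1.1% (0.03 to 6.0%) |

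The documents do not say how often a subject crosses a threshold only at an unscheduled test. For an assumed rate p, the chance of at least one such subject among n is 1 - (1 - p)^n:

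| Assumed p | n = 30 | n = 90 |
|---|---|---|
| 0.5% | 14% | 36% |
| 1% | 26% | 60% |
| 2% | 45% | 84% |
| 5% | 79% | 99% |

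**5. The late testosterone sample.** SAP 7.1.3.1 allows for a 10-25% afternoon fall. Assume, which the documents do not state, that this fall applies to any sample after 11 am. Then 300/0.90 = 333 and 300/0.75 = 400, so a morning value from 300 up to 333 (10% fall) or 400 ng/dL (25% fall) could read below 300 and score as not normalised.

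**The case against.** The strongest reply is that little is hidden. A subject who triggers the repeat from a scheduled sample is already counted up to 5xULN for that enzyme. Under Protocol 12.1.4 an abnormality that interrupts study drug is a reportable adverse event, adverse events are tabulated, and every value is listed. If drug is stopped, an end-of-treatment visit follows within 7 days. The liver table is descriptive and all analyses are exploratory.

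Much of this is true, and it limits the size of the problem. It does not close the gap. The lower levels are safe, but the combined criterion, the bilirubin levels and the 10xULN level are not. An adverse-event term does not fill a cell of the liver table, a listing gives no count by arm, and a peak may have passed by the end-of-treatment visit.

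A reader might also infer more than the documents support:

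- **That valid testosterone retests are discarded.** Nothing says a retest is filed as unscheduled. With visit windows of ±2 days, a prompt retest could be entered under its scheduled visit. What is missing is a rule for choosing between two values.
- **That creatinine and haematocrit repeats bias the tables.** The SAP's laboratory section has no maximum or threshold count for either, so the restriction costs nothing there.
- **That testosterone peaks are lost at confirmatory repeats.** The protocol has no such repeat.
- **That unscheduled values can enter no table at all.** The definitions of baseline (8.1.5) and of last observation carried forward (7.2.1) use the last non-missing value, with no limit to scheduled visits.

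**Conclusion.** The point holds for the liver counts. The SAP states a rule without exception, and on one pathway written into the protocol that rule excludes the first test at which the combined ALT/AST and bilirubin criterion could be met. Any error is downward. The testosterone at-least-once and overall-maximum counts carry the same restriction, which does not match the period of their endpoint, but with less practical consequence.

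The conclusion assumes that the 48-hour repeat is recorded as an unscheduled visit. If it were entered under the scheduled visit, the SAP would still lack a rule for two laboratory values at one visit, and the same-visit pairing would become ambiguous. The frequency is unknown: one subject per arm is an illustration, not an estimate.

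The testosterone retest is a secondary clarification. If the retest is filed as unscheduled, 8.1.7 leaves the late sample in the normalisation analysis. Carrying forward does not help, because the visit value is not missing. If the retest is filed under the visit, no rule selects the value. This should be corrected before the tables are produced; it does not affect the primary bone-density analysis.

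**What to change.** - **SAP 8.1.7:** keep by-visit summaries on scheduled visits. Add that the liver-threshold and potential Hy's-law counts, and the testosterone at-least-once and overall-maximum counts, use all post-baseline results, scheduled and unscheduled. Repeat this with a short cross-reference in 7.1.4.5, 8.6.3.4 and 8.7.5.2.
- **SAP 7.1.4.5 and 8.7.5.2:** pair ALT/AST and bilirubin from the same sample date, so that an off-schedule draw can be assessed.
- **SAP 8.1.6:** add that a valid testosterone retest drawn before 11 am replaces the late sample for that visit, however the retest is recorded.

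The cost is a few sentences and minor programming, with no new data. Safety counts may look slightly less favourable, and by-visit summaries change only where a valid testosterone retest replaces a late sample.
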